# Proprietary Information of MD Anderson

Protocol No: 2019-1008

Version No: 04

Version Date: August 31, 2021

Disease **recurrence** will be determined by surgical pathology (if available) or at least three months of imaging follow-up. Imaging findings will be considered recurrent disease in a lesion if:

1. The lesion was originally considered to be a treatment responder.
2. The lesion showed a successive increase in the size of 25% from nadir or a single imaging time point increase of 40%. (see section 5.1)

Lesions that show an increase in size, but do not meet these criteria will be considered radiation necrosis.

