Current MR imaging protocols for brain metastasis evaluation rely on contrast-enhanced T1-weighted MRI (CE-T1WI), which has proven itself a valuable tool for the visualization of tumor margins. However, changes in lesion size as determined by CE-T1WI images taken alone are not specific to cell death. There has been more success with quantitative MR methods, such as the apparent diffusion coefficient (ADC), which increases with apoptosis and has been correlated with response to therapy. It has also been shown that low pretreatment ADC values are correlated with a favorable response. However, given that ADC is sensitive to many changes in tissue micro-structure, it is often difficult to distinguish between tumor necrosis, edema, or

radiation-induced inflammation, which inhibits its use in monitoring cancer treatment.

Advanced imaging techniques currently in clinical use such as dynamic contrast enhancement perfusion imaging and dynamic susceptibility contrast perfusion imaging have been shown to improve diagnostic accuracy in the assessment of brain metastasis behavior following stereotactic radiosurgery. However, their diagnostic yield is not ideal (sensitivity and specificity less than 90% in clinical trial settings) and their usage is demonstrated in the reactionary scenario following the development of abnormal conventional imaging. These techniques have not been shown to be able to predict future behavior of lesions prior to the development of anatomic imaging abnormalities.

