## 4.4 Contrast Administration

- 4.4.1 Iodinated contrast for acidoCEST imaging: Up to 120 mL of iopamidol using weight based MDACC scale.
  - 4.4.1.1 Patients with history of allergy or adverse reaction to iodinated contrast will not receive iodinated contrast or acidoCEST imaging. They will receive APT CEST imaging only.
- 4.4.2 Gadolinium-based contrast: Gadolinium dosing will be performed per MDACC standard-of-care protocol for advanced brain tumor imaging including a unit dose preceding DCE perfusion imaging and a second unit dose preceding DSC perfusion imaging.
- 4.4.2.1 Patients with history of allergy to gadolinium-based contrast will be excluded from enrollment per section 3.2 of the protocol (Exclusion criteria).

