## 7.3 Analysis Plan

Patients are expected to have on average four brain lesions each. The primary analysis will be performed on the largest lesion within patients at baseline, and secondary analyses will consider all lesions. The sensitivity of each method at detecting lesions as determined by T1 weighting will be reported with 95% confidence intervals. Analyses will also be performed at the subsequent scans as numbers permit.

For the secondary endpoints that consider treatment response, for each of the imaging methods, at each time point, we will calculate the contrast to noise ratio (CNR) in patients with lesions that respond to treatment and in patients with local failure and will compare these by using a Wilcoxon rank-sum test. If numbers permit, analyses may be repeated using all lesions. Additionally, of the lesions that initially respond, some will subsequently grow in size after the initial response. Of these, some will be considered treatment change and some residual disease. The CNR will be compared between lesions with treatment change and those that are progressive disease using a Wilcoxon rank-sum test.

All statistical tests will be performed with two-sided tests with 5% Type I error rates. No adjustment will be made for the multiplicity of testing. We recognize that the Type I error rate overall will be greater than 5%.

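### Recurrence is labelled by pathology in some lesions and by a growth rule in the rest, then pooled in one test. If surgery is chosen partly on rCBV, the DSC comparison can show a spurious association.

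*Combined protocol and SAP*

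**What the plan says.** Section 7.1 states that recurrence "will be determined by surgical pathology (if available) or at least three months of imaging follow-up". Under the imaging route, a lesion that first responded is recurrent if this holds: "The lesion showed a successive increase in the size of 25% from nadir or a single imaging time point increase of 40" per cent. For the rest, "Lesions that show an increase in size, but do not meet these criteria will be considered radiation necrosis".

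Section 7.3 then states: "The CNR will be compared between lesions with treatment change and those that are progressive disease using a Wilcoxon rank-sum test". It adds: "All statistical tests will be performed with two-sided tests with 5% Type I error rates". It does not ask for the label source to be recorded or used.

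On whether the treating team sees DSC, four places matter:
- Section 4.4.2 describes gadolinium dosing under the institution's standard protocol, with one dose before DCE "and a second unit dose preceding DSC perfusion imaging".
- Section 2.1 refers to "Advanced imaging techniques currently in clinical use such as dynamic contrast enhancement perfusion imaging and dynamic susceptibility contrast perfusion imaging" and credits them with better diagnostic accuracy after radiosurgery.
- Objective 1.2.2.4 tests GESE DSC against standard GE DSC for separating necrosis from progression.
- Section 4.3 lists GESE DSC among the study sequences and does not name DSC among the conventional ones.

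The documents do not say how regrowing lesions come to surgery, whether perfusion results are available when that is decided, or how accurate the growth rule is.

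**The concern.** Two references with different error rates feed one label. If the marker under test influences which reference a lesion receives, then marker, route and label become linked even when the marker says nothing about the tissue. This is differential verification. It is a separate matter from the accuracy of the growth rule, because the same imperfect rule applied to every lesion would leave a no-information marker at the 5% level.

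DSC is the marker for which the link is plausible, since the protocol itself describes it as in clinical use after radiosurgery. At stake is the reading of objective 1.2.2.4: an association produced partly by the choice of reference could be taken as evidence that DSC separates necrosis from progression. More lesions would not cure this, because the false-positive rate rises with their number.

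**Working it through.** **The plan's own figure.** Section 7.2 gives one design figure, a 95% interval of at most 14.5 points either side with 50 patients. The exact (Clopper-Pearson) interval at 25/50 is 0.355 to 0.645, a half-width of 14.47 points, so the figure reproduces. It concerns baseline sensitivity. No figure is given for the necrosis-versus-progression test.

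**Inputs from the documents.** 50 patients (3.3) with an average of 4 lesions (7.2, 7.3) give 50 × 4 = 200 lesions; a two-sided 5% rank-sum test (7.3).

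**Inputs assumed.** 60 regrowing lesions (60/200 = 30%); half truly recurrent (π = 0.5); marker independent of truth; resection probability s = 30%, 50% or 70% above the median marker value and 10% below it; pathology always correct; lesions independent.

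**Mechanism.** The growth rule calls a share q = π·sens + (1 − π)·(1 − spec) recurrent. Within each half of the marker range, the share labelled recurrent is s·π + (1 − s)·q. With a 30%/95% rule (sensitivity/specificity) and 70% versus 10% resection:
- q = 0.5 × 0.30 + 0.5 × 0.05 = 0.175
- above the median: 0.7 × 0.5 + 0.3 × 0.175 = 0.4025
- below the median: 0.1 × 0.5 + 0.9 × 0.175 = 0.2075

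The proportion above the median is then 0.4025/0.61 = 0.660 among lesions labelled recurrent and 0.5975/1.39 = 0.430 among those labelled necrosis. The AUC of this useless marker is 0.5 + 0.5 × (0.660 − 0.430) = 0.61. At the mild end (40%/95% rule, 30% versus 10% resection), q = 0.225, the shares are 0.3075 and 0.2525, and the AUC is 0.5 + 0.5 × (0.3075/0.56 − 0.6925/1.44) = 0.53. With an 80%/80% rule, q = 0.5 = π, the shares are equal and the AUC is 0.50.

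**Rejection rate of the pooled test, no-information marker** (simulation, 4,000 data sets per setting, 60 lesions):

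| Rule sens/spec | 30% vs 10% resected | 50% vs 10% | 70% vs 10% |
|---|---|---|---|
| 30%/95% | 7.1% | 16.0% | 28.3% |
| 40%/95% | 6.4% | 12.2% | 20.5% |
| 60%/90% | 5.4% | 7.3% | 9.1% |
| 80%/80% | 4.9% | 4.0% | 5.1% |

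At 20 lesions the same model gives 4.7% to 11.4% with the 30%/95% rule, and about 4% to 6.5% with the 60%/90% or 80%/80% rule.

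**A second model** makes surgery logistic in the marker, with 30% operated, π = 0.5 and a 50%/90% rule. At 20, 40 and 80 lesions:
- odds ratio 2 per marker SD: 5.6%, 5.9%, 7.7%
- odds ratio 4: 6.3%, 8.3%, 12.4%
- odds ratio 1 (no link): 4.8% to 5.0%

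More extreme inputs give more. With odds ratio 4, 80% truly recurrent and a 30%/90% rule, rejection is 31.3% at 40 lesions and 57.0% at 80; with only 10% operated it is 10.8% and 18.4%.

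**Candidate remedies.**
- *One reference for every regrowing lesion:* 4.4% to 5.5%. This assumes the rule can be assessed fully in resected lesions. If surgery cuts follow-up short and half of their rule-positive calls are lost, rejection can reach about 17%.
- *Rank-sum test stratified by label source (van Elteren):* about 4% to 5% when surgery depends on the marker alone. When surgery depends on marker and growth, the second model gives 7.8% to 13.8%. In the first model, multiplying the odds of surgery by 4 when the growth rule is met, with an 80%/80% rule, gives 6.7%, 10.6% and 10.0% for the stratified test against 4.5% to 4.9% for the pooled test. Label source is then a common effect of marker and growth, and conditioning on it creates an association.

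**The case against.** The strongest reply is that both necessary conditions are inferred. The protocol does not say that rCBV influences surgery, and it gives no accuracy for the growth rule. Remove either condition and the pooled test keeps its level. This stands, and it is why the point is conditional.

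The size can also be challenged. The 28% needs a rule with 30% sensitivity, 60 regrowing lesions, and 40% of them resected overall ((70 + 10)/2). This stands too: 28% is the upper end of an assumed range and should not be read as a forecast.

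The calculation also does not match objective 1.2.2.4 exactly. That objective compares GESE with GE, whereas the check takes one uninformative marker; the effect on the GESE-minus-GE difference was not computed. Section 2.1 already holds that DSC is informative, so an uninformative marker is a test case and not the plan's expectation. Section 7.3 names CNR, while 5.6.2 measures rCBV; the argument applies to whichever DSC value is ranked.

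A reader might infer that all the necrosis-versus-progression objectives are affected. The documents do not support that. CEST, Adv Diff and Adv ASL are study sequences (4.3), and nothing says their results guide care.

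One defence fails. Section 7.3 says "No adjustment will be made for the multiplicity of testing" and accepts an overall error rate above 5%. That concerns the number of tests and does not cover bias inside a single one.

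**Conclusion.** The point holds in a limited form. Pooling two references leaves the DSC necrosis-versus-progression comparison open to a spurious association if two things are true: surgery depends partly on rCBV, and the growth rule calls a different share recurrent than pathology would. In the main table and its 20-lesion rerun, rejection at a nominal 5% runs from about 5% to about 28%; harsher assumptions give more, and several plausible settings give none. The lesion count, resection rates and rule accuracy are all assumed, and clustering of lesions within patients is not modelled.

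A reader might go further and conclude that the planned test is invalid, or that stratifying by label source would repair it. Neither follows. The documents do not establish the two conditions, and the stratified test rejects in about 7% to 14% when surgery depends on both marker and growth. Since this is a secondary comparison with no decision rule attached, the point is a cheap improvement to the analysis plan.

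**What to change.** In section 7.3:
1. Record for each regrowing lesion whether the label came from pathology or from imaging.
2. Keep the pooled rank-sum test, and report the necrosis-versus-progression results separately for pathology-labelled and imaging-labelled lesions.
3. Add a sensitivity analysis that applies the imaging rule to every regrowing lesion. Flag and count resected lesions whose follow-up before surgery is too short for the rule to be assessed; do not count them as necrosis by default.
4. Conclude that DSC separates the groups only if the result is consistent across these analyses.
5. If a test stratified by label source is shown, present it as a further sensitivity analysis and not in place of the pooled test.

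It would also help to state in the protocol whether the treating team sees the DSC results, since the size of the concern depends on it.

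The cost is one extra data field and a few sentences. The downsides are small strata with wide uncertainty, and some resected lesions that the imaging rule cannot classify. If the label source is not captured prospectively, recovering it later means returning to the source records.

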#### 1.2.2 Treatment Response:

- 1.2.2.1 Quantitative MRI: To assess the trend of idealized quantitative T1 and T2 values of brain metastases compared to normal brain parenchyma following treatment with stereotactic radiosurgery.
- 1.2.2.2 Chemical Exchange Saturation Transfer (CEST) MRI: To assess the ability of CEST imaging to differentiate radiation necrosis from progressive disease in brain metastases following stereotactic radiosurgery.

- 1.2.2.3 Multiple B Value Diffusion Imaging (Adv Diff): To assess whether Adv Diff can differentiate radiation necrosis from progressive disease in brain metastases following stereotactic radiosurgery.
- 1.2.2.4 Gradient- and Spin-Echo DSC perfusion imaging: To assess whether GESE DSC improves differentiation of radiation necrosis from progressive disease in brain metastases following stereotactic radiosurgery compared to standard GE DSC.
- 1.2.2.5 Multiple inversion time (TI) arterial spin labeling (ASL) “Adv ASL” perfusion imaging: To assess the ability of Adv ASL to differentiate radiation necrosis from progressive disease in brain metastases following stereotactic radiosurgery.

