# **7 STATISTICAL CONSIDERATIONS**

## **7.1 Definitions**

Brain metastases “**treatment response**” will be defined by size and contrast to noise ratio (CNR).

Size – treatment response in a lesion will be considered as a decrease in size of 30%. (see section 5.1)

CNR—treatment response will be considered as a decrease in T1 post-contrast CNR of at least 20% (see section 5.2) by standard T1 post contrast imaging for a lesion.

Metastases that do not meet these criteria for treatment response will be considered treatment failure.

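### On imaging alone, a lesion that never responds and then grows is labelled both treatment failure and radiation necrosis in 7.1, and 7.3 leaves it out of the necrosis-versus-progression test

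*Combined protocol and SAP*

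**What the plan says.** Section 7.1 sorts lesions in two ways.

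- **Response.** There is a size limb, "treatment response in a lesion will be considered as a decrease in size of 30" per cent, and a CNR limb, "treatment response will be considered as a decrease in T1 post-contrast CNR of at least 20" per cent. The section names size and CNR together but does not say outright whether both limbs are needed or either is enough. For all other lesions: "Metastases that do not meet these criteria for treatment response will be considered treatment failure".
- **Growth.** Recurrence is settled by surgical pathology, where there is any, or by three months or more of follow-up scans. The imaging route has two criteria. The first is "The lesion was originally considered to be a treatment responder". The second is a successive 25% rise from nadir, or a 40% rise at one time point. The residual rule follows: "Lesions that show an increase in size, but do not meet these criteria will be considered radiation necrosis".

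Section 7.3 plans two CNR comparisons under treatment response. The first sets responders against local failures. The second sets treatment change against progressive disease, and its population is introduced as "of the lesions that initially respond, some will subsequently grow in size after the initial response". Both of its groups come from that set.

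Objectives 1.2.2.2, 1.2.2.3 and 1.2.2.5 ask whether CEST, Adv Diff and Adv ASL can "differentiate radiation necrosis from progressive disease in brain metastases following stereotactic radiosurgery". Objective 1.2.2.4 asks whether GESE DSC does this better than GE DSC. None is limited to lesions that first responded.

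**The concern.** The residual sentence covers every growing lesion that misses the recurrence criteria, and one way to miss them is never to have responded. A lesion that radiosurgery did not control therefore has no imaging route to the progressive label, whatever its growth rate. It receives the necrosis label by default, beside the treatment-failure label it already holds. Two analysts could classify the same lesion differently and both cite 7.1.

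Section 7.3 does not resolve this. It keeps such lesions out of the one test that addresses necrosis versus progression. What is at stake is the meaning of four secondary objectives: the planned test evaluates the markers only on regrowth after response, while the objectives speak of progressive disease after radiosurgery in general.

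**Working it through.** The plan gives no figure on this point, so the check is one of logic: apply the 7.1 rules to example lesions and see which labels result.

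**Inputs from 7.1:** size response at a 30% fall; CNR response at a fall of at least 20%; growth thresholds of 25% from nadir (successive) or 40% (single time point); prior response required on imaging; residual label for all other growth. **Input from 7.3:** the second comparison is restricted to initial responders.

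**Assumptions:** lesion sizes and CNR courses are illustrative. Local failure in 7.3 is read as treatment failure in 7.1, and treatment change in 7.3 as radiation necrosis in 7.1.

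| Lesion | Size (mm) | CNR | Response status | Growth label | In second 7.3 test |
|---|---|---|---|---|---|
| A | 10, 13, 17, 22 | flat | failure | radiation necrosis | no |
| B | 10, 8, 10.5, 14 | falls at most 5% | failure | radiation necrosis | no |
| C | as A, tumour proven by pathology | flat | failure | recurrence | no |
| D, both limbs needed | as A | falls 25% | failure | radiation necrosis | no |
| D, either limb enough | as A | falls 25% | responder | recurrence | yes |
| E | 10, 6, 7, 9 | falls 30% | responder | recurrence | yes |
| F | 10, 6, 6.3, 6.6 | falls 30% | responder | radiation necrosis | yes |
| G | 10, 11.5 | flat | failure | radiation necrosis | no |

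Growth from nadir:

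- A: (22 − 10)/10 = 120%.
- B: (14 − 8)/8 = 75%, after a fall of (10 − 8)/10 = 20%, short of the 30% limb.
- E: (9 − 6)/6 = 50%.
- F: (6.6 − 6)/6 = 10%.
- G: (11.5 − 10)/10 = 15%.

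Reading the table:

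1. A and B meet the second recurrence criterion but are barred by the first. They are failure and necrosis whichever way the two response limbs are combined.
2. C shows that pathology rescues the label but not entry to the 7.3 test.
3. D shows that the CNR limb matters: the same sizes give opposite labels under the two readings of response.
4. E and F show that among initial responders 7.1 and 7.3 agree.
5. If the first criterion is simply deleted, A and B become recurrence but stay outside the 7.3 test. G does not change: 15% is below both thresholds, so it is still failure and necrosis. Deletion alone is not a remedy.

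**The case against.** A fair defence has five parts.

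- **Pathology is a separate route.** The two numbered criteria govern imaging findings only, so it would be wrong to infer that the first criterion bars a never-responder from recurrence altogether. This stands. Such a lesion misses the second comparison because of 7.3's own population.
- **Response also has a CNR limb.** A reader might infer that any lesion that never shrinks 30% is a non-responder. That does not follow if either limb is enough (lesion D). This narrows the affected set; lesions that grow with stable or rising CNR remain in it on either reading.
- **The planned test is not contaminated.** A reader might infer that primary progressors are counted as necrosis in the 7.3 test. Read strictly, they are in neither group, because both are drawn from initial responders. Mislabelling would bite only if the 7.1 label were used outside that population, for instance to report on the wider objectives.
- **These lesions are not discarded.** They enter the first comparison as local failures. That is true, but that group also holds stable lesions and lesions that shrank just short of the threshold, so it cannot answer the necrosis-versus-progression question.
- **Early growth is not shown to be the surest progression.** Section 2.1 itself warns that size change on contrast-enhanced T1 images does not by itself establish whether cells have died. The documents give no ground for ranking early growth above regrowth as evidence of tumour. Regrowth after control is a coherent, narrower target.

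What is left is the double label on imaging and a test narrower than its objectives.

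**Conclusion.** The concern holds in this form. Judged by imaging, a lesion that never meets the response definition and then grows is both treatment failure and radiation necrosis, even above the 25% and 40% thresholds. The necrosis-versus-progression test excludes it, with or without pathology, although objectives 1.2.2.2 to 1.2.2.5 do not. This rests on the literal wording of 7.1 and 7.3 and on the matching of terms stated above.

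The number of lesions cannot be derived, because the documents give no response or growth rates. A reader might be tempted to supply them. With response rate r, growth rate gN in non-responders and regrowth rate gR in responders, the never-responder share of growing lesions is (1 − r)gN / [(1 − r)gN + r·gR]. Assuming r = 0.7, gN = 0.2, gR = 0.3 gives 0.06/0.27 = 22%; assuming 0.5, 0.4, 0.2 gives 0.20/0.30 = 67%. The spread reflects the assumptions and is no estimate for this trial.

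This should be fixed, but it does not threaten the trial's main result: only secondary comparisons without multiplicity adjustment are affected, and the primary endpoints (baseline sensitivity) are not.

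**What to change.** **In 7.1:**

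- State that response status (responder or failure) and cause of growth (progression or necrosis) are two separate classifications.
- Limit the residual necrosis sentence so that it cannot apply to a never-responder whose growth meets the second recurrence criterion. Give such lesions a progressive-disease label that does not depend on prior response.
- State one label for never-responders that grow below the thresholds (lesion G).
- State whether response needs both limbs or either.

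**In 7.3:** keep the comparison in initial responders, and add the same comparison in all treated lesions that grow, reported by earlier response status. If the sponsor prefers not to add it, restrict the stated conclusion to regrowth after response.

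**Cost:** wording in two sections, settled before lesions are classified, with no new scans or data. The downside is a more mixed progressive group in the added analysis, since some early growth may be necrosis; reporting by earlier response status shows this openly.

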## 4.5 Imaging Time Points

- 4.5.1 The baseline study scan will be performed within the fourteen (14) days **before** scheduled brain radiation treatment.
- 4.5.2 Seven additional study scans will be performed on the schedule of the patient's clinical protocol, but not less than four (4) weeks apart and not more than 16 (sixteen) weeks apart.

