## 4.6 Conclusion of Study Participation:

- 4.6.1 Completion of eight (8) study scans.
- 4.6.2 Upon patient request.
- 4.6.3 A contraindication to further MR imaging.
- 4.6.4 Death.

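### The imaging rule for recurrence counts scans while spacing may vary from 4 to 16 weeks, and it has no provision for later regression, so a transient swelling's label can depend on scan schedule

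*Combined protocol and SAP*

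**What the plan says.** Section 7.1 (Definitions) says that recurrence "will be determined by surgical pathology (if available) or at least three months of imaging follow-up". On imaging, two conditions are listed. The first is "The lesion was originally considered to be a treatment responder". The second is "The lesion showed a successive increase in the size of 25% from nadir or a single imaging time point increase of 40" per cent. The remaining growing lesions are handled by default: "Lesions that show an increase in size, but do not meet these criteria will be considered radiation necrosis".

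Section 4.5.2 puts the seven follow-up scans on the patient's clinical schedule, "not less than four (4) weeks apart and not more than 16 (sixteen) weeks apart". Under section 4.6, participation ends at "Completion of eight (8) study scans", if not sooner for another listed reason.

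Section 7.3 then uses the label: "The CNR will be compared between lesions with treatment change and those that are progressive disease using a Wilcoxon rank-sum test". I take its progressive disease group to be the recurrent lesions of 7.1, and its treatment change group to be the radiation necrosis lesions. The plan does not state this mapping.

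**The concern.** Both parts of the size criterion are expressed in scans, not in weeks. *Successive* needs more than one scan, and the 40% limb needs a scan to fall near the peak. With spacing free to differ fourfold between patients, the same course of growth is sampled differently. The plan does not standardise assessment times or adjust for spacing. It does not define *successive* or say which scan the 40% is measured from. It is also silent on a lesion that meets the criterion and then falls back without treatment, although such a course would suggest treatment effect rather than progression.

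At stake is the reference label for the objectives on separating radiation necrosis from progressive disease (1.2.2.2 to 1.2.2.5). Transient swellings placed in the progressive group mix the two groups in the CNR comparison, to a degree that may differ with scan density. The primary baseline conspicuity endpoint does not use this label.

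**Working it through.** **The plan's own figure.** The plan gives no sample size, power or effect size for this comparison. Its one computed design figure, the 14.5% half-width in section 7.2, belongs to the primary sensitivity endpoint. It reproduces (exact interval at 25/50: 35.5% to 64.5%, half-width 14.47%) and does not enter here.

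**Inputs from the documents.** The 25% and 40% thresholds (7.1); spacing of 4 to 16 weeks (4.5.2); eight scans (4.6), so seven intervals.

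**Assumptions, because the documents give none.** A responder at its nadir swells linearly for *u* weeks to a peak of *P*% above nadir, then returns linearly over *u* weeks. Diameters are error-free, and every phase of the scan grid is equally likely.

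**Readings of the criterion.**
- Reading 1: two consecutive rises ending at least 25% above nadir, or any scan at least 40% above nadir.
- Reading 2: two consecutive scans at least 25% above nadir, or any scan at least 40% above nadir.
- Reading 3: two consecutive steps of at least 25% each, or one step of at least 40%, each measured from the preceding scan.

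**Central case, *u* = 12, *P* = 35.** The 40% level is never reached, so only the 25% limb matters.

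- *Reading 1, 4 weeks.* Let *t* be the last scan more than 8 and at most 12 weeks after onset. If *t* is below 10, the next scan is higher still, at 35 × (20 − *t*)/12, which exceeds 29%. If *t* is 10 or more, the scan itself is at least 35 × 10/12 = 29.2%. An earlier rise precedes it either way. Result: 100%.
- *Reading 1, 16 weeks.* Two rises need scans at *t* and *t* + 16 with the second higher, so *t* < 4. The second value is 35 × (8 − *t*)/12, below 35 × 8/12 = 23.3%. The 25% level is not reached. Result: 0%.
- *Reading 2.* Time spent at or above 25% is 2 × 12 × (1 − 25/35) = 6.86 weeks. The chance that two consecutive scans fall inside is (6.86 − 4)/4 = 71% at 4 weeks (72% when counted over 400 phases) and zero at 16 weeks, because 16 exceeds 6.86.

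At 16-week spacing this 24-week swelling always shows some growth, so it becomes radiation necrosis by default.

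**Other cases, share labelled recurrence at 4 / 8 / 16 weeks.**

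| Reading | *u* (weeks) | Peak | 4 | 8 | 16 |
|---|---|---|---|---|---|
| 1 | 12 | 30% | 100% | 50% | 0% |
| 1 | 12 | 35% | 100% | 86% | 0% |
| 1 | 12 | 45% | 100% | 100% | 25% |
| 1 | 16 | 45% | 100% | 100% | 56% |
| 1 | 24 | 45% | 100% | 100% | 100% |
| 2 | 12 | 30% | 0% | 0% | 0% |
| 2 | 12 | 35% | 72% | 0% | 0% |
| 2 | 12 | 45% | 100% | 67% | 17% |
| 3 | 12 | 60% | 0% | 0% | 50% |

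Two entries by hand. Reading 2, 45% peak, 16 weeks: time above 40% is 24 × (1 − 40/45) = 2.67 weeks, and 2.67/16 = 17%. Reading 3, 60% peak: at 4 weeks the largest step is from nadir to +20%, short of 25%. At 16 weeks a scan lands at +40% or more for 24 × (1 − 40/60) = 8 weeks of phase, with the preceding scan at nadir, so 8/16 = 50%.

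**Shape.** A raised-cosine swelling lasting 24 weeks with a 35% peak gives 100% at 4 weeks against 0% to 2% at 16 weeks, under Readings 1 and 2 and their variants with the 40% taken from the preceding scan.

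**Follow-up length.** Seven intervals span 7 × 4 = 28 weeks at the closest spacing and 7 × 16 = 112 weeks at the widest. Three months, about 13 weeks, covers three 4-week intervals (12 weeks) but less than one 16-week interval.

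**The case against.** A reader might infer that the label is final once the criterion is met. The documents do not say so: 7.1 states neither permanence nor reversal. Its governing sentence rests the determination on pathology where available, or on at least three months of imaging. What stands is narrower. What those months must show is unstated, and no rule covers regression after the criterion is met.

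A reader might also infer that any transient swelling is recurrence at 4-week spacing and radiation necrosis at 16-week spacing. The table does not support that. Large or long swellings can be recurrence at both spacings, a 30% peak is never recurrence under Reading 2, and Reading 3 reverses the direction for a 60% peak. A brief swelling can fall between 16-week scans and receive neither label.

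Third, it is tempting to say that clinical suspicion drives the label through earlier rescanning. Spacing does follow the clinical schedule, but the documents do not report whether worrying lesions are scanned sooner.

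Finally, swelling size, shape and duration are assumed here, and 4.5.2 gives a permitted window, not the spacing patients will actually have. These objections limit the size and generality of the point. They do not remove the dependence on spacing or the missing regression rule.

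**Conclusion.** The concern holds in this limited form. The imaging label depends on scan spacing and on undefined wording, the plan does not control for either, and it does not say how later untreated regression is handled. In the central case the chance of a recurrence label moves from 100% or 72% at 4-week spacing to 0% at 16-week spacing, depending on the reading. Those figures rest on the assumed triangular course, error-free diameters and random scan phase. They illustrate the sensitivity of the rule and do not estimate a misclassification rate.

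The consequence is possible misclassification in the secondary comparison of treatment change with progressive disease, for lesions without pathology. The net bias in CNR cannot be computed, because the documents give no distribution of scan spacing, swelling course or recurrence rate. The plan should be amended on this point, but the primary endpoint is unaffected.

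**What to change.** These changes concern analysis labels only. They alter neither care nor the scan schedule.

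- **In 7.1**, define *successive*, and name the reference scan for the 40% increase. Then add: absent pathology, a lesion that meets the size criterion and later falls back below 25% above nadir, confirmed on the next study scan where one exists, with no intervening local or new systemic treatment, is analysed as treatment change. The confirmation guards against one noisy diameter reclassifying a true recurrence.
- **In 7.3**, report the CNR comparison with and without this reclassification. Add a sensitivity analysis for scan spacing as numbers permit, for example by re-deriving labels on a common thinned scan grid. Formal stratification by spacing is likely to be too thin in the regrowing subset of 50 patients.

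**Cost.** The wording is cheap and uses existing scans, but labels can be set only at the end of follow-up, and intervening treatment must be abstracted from the record. Lesions with no scan after the swelling keep the label given by the size criterion and should be counted and reported. This matters most in densely scanned patients. At 4-week spacing, the central swelling starting at week 16 reads +12%, +23% and +35% at weeks 20, 24 and 28. It meets Reading 1 on the eighth and last scan, so regression could not be seen.
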